10.2.2 Analysis of Secondary Endpoints

The secondary endpoints include:

- Change in Plasma levels of Immunological Factors and Frequencies of IFN γ and IL-17 MBP-specific PBMC at months 3, 6, 9 and 12 compared with baseline
- MSFC 3 dimensional composite z-score at every 3 month time point through 2 years compared to baseline
- Expanded Disability Status Scale (EDSS) score at every 3 month time point through 2 years compared to baseline
- Percentage of subjects with improvement (as defined for the primary endpoint) at months 3, 6, 9 and 12 compared to baseline
- Occurrence of clinical relapse at any point in the study

- Interval change in T2 lesion number and volume on MRI scans obtained at months 6 and 12 compared to baseline
- The number and volume of gadolinium enhancing lesions on MRI scans obtained at months 6 and 12 compared to baseline
- Interval change in the number and volume of gadolinium enhancing lesions on MRI scans obtained at months 6 and 12 compared to baseline.
- Toxicity and Adverse events in both arms

For continuous outcomes, two-sample t-tests or Wilcoxon rank sum tests will be used to compare the treatment arms. For categorical outcomes, Chi-square tests or Fisher's exact test will be used to compare the treatment arms. The proportion of subjects who experience adverse events and serious adverse events will be summarized by treatment group descriptively; no inferential tests will be performed.

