2.2 Secondary Objectives

- To assess the effect of ECP versus corticosteroids on plasma levels of immunological factors and the frequency of circulating myelin-reactive Th1 and Th17 cells
- To determine whether changes in immunological parameters that occur following initiation of ECP or corticosteroids correlate with clinical outcomes
- To assess the impact of ECP versus corticosteroids on Expanded Disability Status Scale (EDSS) scores every 3 months through 2 years compared to baseline
- To assess the impact of ECP versus corticosteroids on MSFC three dimensional composite z-score every 3 months through 2 years compared to baseline
- To assess the effect of ECP on risk of clinical relapse
- To assess the effect of ECP versus corticosteroids on the frequency of gadolinium-enhancing T1 weighted lesions on cranial MRI scans obtained at months 6 and 12 compared to baseline
- To assess the effect of ECP versus corticosteroids on interval changes in T2 weighted lesion number and volume at months 6 and 12 compared to baseline.
- To assess the tolerability and the safety profiles of ECP versus corticosteroids

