5. PATIENT WITHDRAWAL AND REPLACEMENT

Patients may withdraw from the study at any time without penalty and for any reason without prejudice to his or her future medical care.

Patients must be withdrawn under the following circumstances:

- The patient withdraws consent
- Pregnancy (see Section 8.2.2.9)
- Unacceptable toxicity including patients on corticosteroids who develop psychosis or aseptic necrosis of the femoral head

Patients may be required to withdraw after discussion with the investigator for the following reasons:

- AE(s)
- At the discretion of the investigator
- Violation of eligibility criteria
- Deviation from the treatment plan specified in the protocol (e.g., incorrect administration of the study drug, failure to attend study visits, etc.)
- The treating physician can withdraw the patient from the study at any time and for any medical reason that he/she deems necessary
- The patient has a right to withdraw at any time, for any medical or other reasons.
- Patients who experience a clinical relapse (defined as neurological event characterized by new or worsening symptoms lasting 48 hours after a stable period of at least 30 days and is considered in the judgment of the investigator to be a clinical relapse). Patients who fail therapy will be off study, and further therapy will be at the discretion of the treating neurologist. The study will not cover any form of therapy after the patient is off study.
- Patients who have interval accumulation of T1 or T2 lesions and/ or gadolinium enhancing T1 lesions on the month 6 MRI scan
- In all cases, the reason(s) for withdrawal, and the primary reason, must be recorded on the case report form (CRF) or similar.

Withdrawn patients will be replaced.

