8.2.2.2 Definitions

An AE is any untoward medical occurrence that occurs in a patient or clinical investigation subject administered a pharmaceutical product, and which does not necessarily have to have a causal relationship with this treatment. An AE can therefore be any unfavorable and unintended sign (including a clinical significant abnormal laboratory finding), symptom, or disease temporally associated with the use of an investigational product, whether or not considered related to the product.

All AEs, including intercurrent illnesses, occurring during the study will be documented in the CRF. Underlying disease worsening (MS), hospitalization for routine study activities, and abnormal laboratory results associated with MS, will not be considered as AEs. Relapse of underlying malignancy will not be considered as an AE/SAE but will be captured and analyzed separately. MS will not be considered as an AE, unless it meets any of the seriousness criteria, in

particular hospitalization or death. Concomitant illnesses, which existed prior to entry into the study, will not be considered AEs unless they worsen during the treatment period. Pre-existing conditions will be recorded in the CRF on the Medical History or appropriate page. AEs will be captured after informed consent signed until 30 days post the completion of the last intervention. (Week 52).

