10.4 Determination of Sample Size

Assuming that the proportion of subjects in the corticosteroid treatment who show no evidence of clinical progression at 52 (12 months) is 30%, 66 subjects (33 per treatment arm) provides at least 80% power to detect a treatment difference of 30% (i.e., 60% of the ECP treated subjects will show no evidence of clinical progression at 12 months), based on the normal approximation of the binomial distribution and a one-sided Type I error of 5%.

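### Relapse and adverse events are summarised as crude proportions with no allowance for observed time, although follow-up can end early and may differ by arm

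*Combined protocol and SAP*

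**What the plan says.** Section 2.2 sets the relapse objective: "To assess the effect of ECP on risk of clinical relapse". Section 10.2.2 turns it into "Occurrence of clinical relapse at any point in the study" and assigns chi-square or Fisher's exact tests to categorical outcomes. For safety the same section says: "The proportion of subjects who experience adverse events and serious adverse events will be summarized by treatment group descriptively", with no inferential test. It gives no person-time rate, time-to-event method or censoring rule for either outcome. The only drop-out rule, in Section 10.2.1, covers the primary endpoint.

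Several sections bear on how long a patient is observed:

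- Section 5 lists reasons for which a patient may be required to withdraw. They include AEs, investigator discretion, deviation from the treatment plan, clinical relapse and new lesions on the month-6 MRI. Inside the relapse item it adds: "Patients who fail therapy will be off study, and further therapy will be at the discretion of the treating neurologist". Failing therapy is not defined.
- Section 3.1 says ECP continues if disability is stable or improved. It states nothing equivalent for the control arm.
- Section 8.2.2.2: "AEs will be captured after informed consent signed until 30 days post the completion of the last intervention". Section 8.2.2.4 gives the end as Week 52 or 30 days after the last intervention. Section 8.2.2.5 records serious AEs (SAEs) until Week 52.
- Section 9.2.8 gives patients who withdraw early one termination visit, with the Week 52 assessments.

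**The concern.** A crude proportion compares risk fairly only if both arms are watched for about the same time. A patient who leaves at month 4 without a relapse counts in the denominator exactly like one followed relapse-free to month 12. If one arm loses patients sooner, its proportions of relapse and AEs fall for that reason alone.

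Some exit routes in Section 5 depend on outcome or on investigator judgement, in an open-label trial with very different treatment burdens. By week 36 the schedule gives 8×3 + 8×2 + 20×1 = 60 ECP procedures against 36/4 = 9 infusions. Equal observation time therefore cannot be taken for granted. At stake are the relapse comparison and the reader's view of comparative safety, which Section 2.2 makes an objective. The primary endpoint is not affected by this point.

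**Working it through.** **Plan's own figure.** Section 10.4 assumes 30% of controls free of progression at 12 months and "60% of the ECP treated subjects will show no evidence of clinical progression at 12 months", with 33 per arm and one-sided 5%. The pooled proportion is 0.45. Null SE = √(2×0.45×0.55/33) = 0.1225; alternative SE = √((0.21+0.24)/33) = 0.1168. Power = Φ((0.30 − 1.645×0.1225)/0.1168) = Φ(0.844) = 80.06%, so the stated 80% reproduces.

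**Illustration.** The documents give no exit rates and no relapse or AE rates. Three things are therefore assumed: a constant progression hazard matching Section 10.4, exit caused only by progression, and the same true event risk in both arms, independent of progression.

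Hazards per year: control −ln 0.3 = 1.204; ECP −ln 0.6 = 0.511.

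*Mean observed time in year 1 if every progressor leaves*

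- Exit at once, (1 − e^(−h))/h: control 0.7/1.204 = 0.581 years (7.0 months); ECP 0.4/0.511 = 0.783 years (9.4 months). Ratio 1.35.
- Exit at the next 3-monthly visit, 3(1 − S)/(1 − S^¼) months, where S is the 12-month progression-free proportion: control 3×0.7/0.2599 = 8.1; ECP 3×0.4/0.1199 = 10.0. Ratio 1.24.

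*If only a share f of progressors leaves.* Mean time is (1 − f) + f×m, where m is the all-leave mean in years.

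| f | Exit at once: control, ECP (years) | Ratio | Ratio, exit at next visit |
|---|---|---|---|
| 1 | 0.581, 0.783 | 1.35 | 1.24 |
| 0.5 | 0.791, 0.892 | 1.13 | 1.10 |
| 0.25 | 0.895, 0.946 | 1.06 | 1.04 |
| 0 | 1, 1 | 1 | 1 |

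With exit at once the ratio passes 1.10 when f is about 0.41, from 1 − 0.217f = 1.1(1 − 0.419f).

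*AE window with the 30-day tail (30/365 = 0.082 years), all leaving at once:* (0.783 + 0.082)/(0.581 + 0.082) = 1.30.

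*Observed proportions with equal true 12-month risk, all progressors leaving (control v ECP)*

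| True risk | Exit at next visit | Exit at once |
|---|---|---|
| 10% | 6.8% v 8.4% | 5.9% v 7.9% |
| 20% | 13.7% v 16.8% | 11.9% v 15.8% |
| 30% | 20.9% v 25.4% | 18.1% v 23.9% |
| 50% | 35.8% v 42.9% | 31.1% v 40.3% |

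For exit at once the formula is h_r/(h + h_r) × (1 − e^(−(h + h_r))), with h_r = −ln(1 − risk). At 20% in controls: 0.223/1.427 × (1 − 0.24) = 11.9%.

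Across these risks, the chance that a two-sided 5% chi-square test with 33 per arm shows ECP significantly worse rises from 2.6%–3.2% with no bias to 4.3%–9.6% (next visit) or 4.8%–12.9% (at once). A person-time or time-to-event analysis gives a ratio of 1 under the same assumptions.

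*Reverse case.* If progression ended observation in the ECP arm only, ECP would have 10.0/12 = 0.83 (next visit) or 9.4/12 = 0.78 (at once) of the control time. A true 20% would then appear as 20% in controls against 16.8% or 15.8% on ECP.

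**The case against.** The strongest case on the other side has five parts.

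1. *The exits are not shown to happen.* Section 10.4 gives progression rates, not exit rates. Disability progression is not among the Section 5 reasons, most of that list is discretionary, and Section 3.1 schedules disability assessments for all subjects through 2 years. This stands, and it makes the ratios above an illustration. It does not supply a method for patients who do leave for AEs, discretion or MRI lesions.
2. *If failing therapy means relapse, the event is counted before the patient goes.* This also stands: under that reading the rule does not shorten relapse observation. It would still shorten AE observation afterwards.
3. *AEs are described, not tested.* True, so no AE test is biased. Readers will still compare the two percentages. If SAEs really are recorded to Week 52 for everyone, their window would not shrink, but the three sections on capture do not agree clearly.
4. *Relapses may be few.* Entry requires none for 2 years. At a true risk of 10% with exit at the next visit, the distortion is 33×0.068 = 2.2 against 33×0.084 = 2.8 patients. The effect is small at low risk and larger for common AEs.
5. *The remedy has limits.* With few relapses a log-rank test gains no power, and it assumes that leaving is unrelated to relapse risk. Both limits are accepted. The crude proportion makes no better assumption; it treats early leavers without a relapse as relapse-free throughout.

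**Conclusion.** The point holds as a gap in method: Section 10.2.2 ignores observed time for two outcomes whose observation can end early. The size is uncertain. It runs from nothing, if no exits differ by arm, to a year-1 ratio of observed time of 1.24 to 1.35 if every progressor in both arms left. It is about 1.13 or 1.06 if half or a quarter left at once. These figures rest on constant hazards, equal and independent event risk, and exit through progression, none of which the documents establish.

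A reader might infer two stronger things. One is that the 30% v 60% assumption means controls will be watched for less time, so ECP will look worse. The documents do not support this: progression is not a stated reason for leaving, failing therapy is undefined and sits in the relapse item, and the only continuation rule tied to disability names ECP, which could reverse the imbalance. The other is that the gap keeps widening to 2 years. Treatment ends at Week 52, Table 2 marks only the two disability measures after month 12, and Section 11.9 gives each patient at most 52 weeks. There is no basis for carrying the same exit hazard through year 2.

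This is a cheap improvement of low to moderate severity.

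**What to change.** In Section 10.2.2:

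- Make the relapse analysis time from randomisation to first relapse, censored at the last relapse assessment, with Kaplan-Meier curves and a log-rank test. Report relapses per person-year and keep the crude proportion as supportive.
- For AEs and SAEs, report rates per person-year from first treatment to the end of the capture window beside the crude proportions, with total observed time by arm.

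Elsewhere:

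- Record relapse onset dates. Table 2 has no relapse item, and Section 8.2.2.2 generally keeps MS worsening out of AE reporting, so a date field may have to be added. AE onset dates are already required by Section 8.2.2.4.
- Reconcile Sections 3.1, 5, 8.2.2.2, 8.2.2.4, 8.2.2.5 and 10.2.2 on what failing therapy means, whether it applies to both arms, and when AE and SAE capture ends.
- Section 5 also replaces withdrawn patients, so state how both the withdrawn patient and the replacement enter the denominators and person-time.

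The cost is plan wording, perhaps one data field and a little more analysis. There is no gain in power if relapses are few, and the assumption that censoring is unrelated to relapse risk should be stated beside the result.

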Dosage and frequency of administration	Study Arm: Weeks 1-8: 3 times per week Weeks 9-16: Twice per week Weeks 17-36: Treatment on two consecutive days every 2 weeks (or optionally, one treatment per week) Weeks 37-44: Once every 2 weeks Weeks 45-52: Once every 4 Weeks Control Arm: Pulsed corticosteroids (1 gm. of MP IV every month) for 52 Weeks.
Duration of Administration	1 year (52 weeks)
Statistical methods	An intent to treat approach will be used. The proportion of subjects who show no evidence of disease progression, as defined above, will be compared between treatment groups using the Chi-square test. Two-sample t-tests or Wilcoxon rank sum tests will be used to assess treatment differences in continuous outcomes and chi-square or Fisher's exact tests will be used for categorical outcomes.
Power and Sample Size	Assuming that the proportion of subjects in the corticosteroid treatment who show no evidence of disease progression at Week 52 is 30%, 66 subjects (33 per treatment arm) provides at least 80% power to detect a treatment difference of 30% (i.e., 60% of the ECP treated subjects will improve at Week 17), based on the normal approximation of the binomial distribution and a one-sided Type I error of 5%.

LIST OF STUDY PERSONNEL

Sponsors	[name]. Director Adult BMT Program and ECP. University of Michigan
Principal Investigator	[name]. Director Adult BMT Program and ECP. University of Michigan [contact]. [contact]
Co-Principal Investigator	[name]. Holtom-Garrett Family Professor of Neurology and Director of Multiple Sclerosis Center, University of Michigan [contact] [contact]
SAE/Adverse Event Reporting	[name] [contact]
Laboratory	University of Michigan Clinical Laboratories for routine studies Neuroimmunology Laboratory, Dept. of Neurology for research studies ([name], Director)

TABLE OF CONTENTS

PROTOCOL SYNOPSIS	4
LIST OF STUDY PERSONNEL	11
TABLE OF CONTENTS	12
LIST OF ABBREVIATIONS AND DEFINITIONS OF TERMS	16
1 INTRODUCTION	18
1.1 Background	18
1.2 Rationale	20
2 STUDY OBJECTIVES	21
2.1 Primary Objective	21
2.2 Secondary Objectives	21
3 OVERALL DESIGN AND PLAN OF THE STUDY	22
3.1 Overview	22
3.2 Endpoints	24
3.2.1 Primary Endpoint	24
3.2.2 Secondary Endpoints	24
3.3 Justification of the Study Design	26
4 STUDY POPULATION	26
4.1 Inclusion Criteria	26
4.2 Exclusion Criteria	27
5 PATIENT WITHDRAWAL AND REPLACEMENT	28
6 TREATMENT	31
6.1 Control Arm: Corticosteroid Treatment	31
6.2 Study Arm: Extracorporeal Photopheresis	31
7 STUDY PRODUCT	31

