7. PASAT-3”

An individual component should be discontinued only if the patient meets the discontinue criteria for that component. Other components should still be administered.

Every effort should be made to use the same testing room and the same designated area for the Timed 25 Foot Walk at every visit. It is essential that that the potential for external distraction be kept to a minimum. If the space designated for the Timed 25 Foot Walk is in a public hallway, complete privacy may be impossible, however, every attempt must be made to keep the patient’s path clear of obstacles (human and inanimate). No one other than the examiner and the patient should be in the testing room during 9-HPT and PASAT. The first time a subject takes the PASAT, practice sequences are initially administered a maximum of 3 times.

The response definitions are as below:

An MSFC score is created from the tests done above. Details can be found in the publication referenced (Fischer et al). The composite consists of Z score from the components tested and compared using normals to standardize the scored. The MSFCS is a continuous variable that can be used as any numerical variable in analyses. The value is subject to tests appropriate for continuous variables, such as t-tests, Analysis of variance and regression analysis as well as nonparametric test. A composite based on such Z-scores can also measure change in performance over time. By computing the composite at one point in time and measuring the patient at a later point in time, the arithmetic difference between MSFC scores can be used to measure improvement or worsening.

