8.1.2 EDSS

The EDSS form can be found in Appendix 2. The scores are calculated from the Functional System Score (FSS). EDSS and FSS will be determined by a single neurologist at baseline, and every 3 months through 2 years.

The EDSS is an ordinal scale with a 0.5-point increments ranging from 0-10.0. (increasing score indicates worsening) and based largely on ambulatory impairment in its middle range (EDSS 4.5-7.5 points).

0= normal neurological exam

10=death due to MS

Score 6 is still ambulatory with assistance

Score of 7 means patient must use a wheelchair.

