11.9 Duration of the Study

For an individual patient, the maximum duration of the study for each patient will be up to 52 weeks (excluding up to 1 week screening). The total study is expected to last 2 years.

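### Secondary MSFC and EDSS comparisons do not use baseline as a covariate and name no key visit (optional improvement)

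*Combined protocol and SAP*

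**What the plan says.** Section 10.2.2 lists the MSFC three-dimensional composite z-score and the "Expanded Disability Status Scale (EDSS) score at every 3 month time point through 2 years compared to baseline" as secondary endpoints. Section 2.2 words the MSFC objective the same way: "To assess the impact of ECP versus corticosteroids on MSFC three dimensional composite z-score every 3 months through 2 years compared to baseline". Table 2 in section 9.1 schedules both tests every 3 months through 2 years.

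The between-arm method in 10.2.2 is: "For continuous outcomes, two-sample t-tests or Wilcoxon rank sum tests will be used to compare the treatment arms". The synopsis repeats it: "Two-sample t-tests or Wilcoxon rank sum tests will be used to assess treatment differences in continuous outcomes". Neither place names a baseline covariate, a repeated-measures model, a key visit or a multiplicity rule for these outcomes. No significance level is set for secondary endpoints. Week 52 is designated only for the primary composite (sections 3.2.1 and 10.2.1).

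Section 8.1.1 says of the MSFC: "The value is subject to tests appropriate for continuous variables, such as t-tests, Analysis of variance and regression analysis as well as nonparametric test". It adds that the arithmetic difference between two MSFC scores can measure improvement or worsening. This describes the scale; section 10 does not turn it into a planned regression. Section 8.1.2 states: "The EDSS is an ordinal scale with a 0.5-point increments ranging from 0-10.0".

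**The concern.** Both outcomes are measured at baseline in every patient, and each patient's later score is likely to be related to the first. A test of change from baseline uses the baseline by subtraction only. Fitting it as a covariate is never less efficient in large samples and costs almost nothing at this size. With 33 patients per arm, precision is scarce.

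The second issue is interpretation. Each outcome yields a series of tests with no stated order of importance. A reader of the report could not tell from the plan which visit carries the MSFC or EDSS result, and the chance that some visit reaches 5% under no effect is well above 5%.

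What is at stake is the clarity and precision of two secondary outcomes in an open-label phase II trial, not the primary test.

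**Working it through.** **Inputs from the documents**
- 66 patients, 33 per arm, 1:1 (section 10.1).
- Visits: 24/3 = 8 per outcome on the 2-year schedule. Section 11.9 says "the maximum duration of the study for each patient will be up to 52 weeks", which would give 12/3 = 4. Both counts are carried below.
- No SD, correlation or power figure is given for MSFC or EDSS.

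**Assumptions**
- Equal variance at baseline and follow-up; results in SD units.
- Baseline-to-follow-up correlation r from 0.5 to 0.9.
- Two-sided 5% per visit.

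**1. The plan's own figure.** The only power statement is for the primary (section 10.4): 30% v 60%, 33 per arm, one-sided 5%, at least 80%. With pooled proportion 0.45, z = [0.30·√33 − 1.645·√(2·0.45·0.55)] / √(0.30·0.70 + 0.60·0.40) = (1.723 − 1.157)/0.671 = 0.844, so power is 80.1%. The figure reproduces, and nothing below alters it.

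**2. Precision at one visit.** The variance of a change score is 2(1 − r), and the ANCOVA residual variance is 1 − r². Their ratio is (1 + r)/2. The 95% half-width is t·√(V·2/33), with 64 df for change and 63 df for ANCOVA. The matching change-score sample size is 33/ratio.

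| r | Variance ratio | Half-width, change | Half-width, ANCOVA | Change-score n per arm matching ANCOVA with 33 |
|---|---|---|---|---|
| 0.5 | 0.75 | 0.492 SD | 0.426 SD | 44.0 |
| 0.7 | 0.85 | 0.381 SD | 0.351 SD | 38.8 |
| 0.9 | 0.95 | 0.220 SD | 0.214 SD | 34.7 |

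The gain is worth about 2 to 11 patients per arm. The formula is for a linear model, so it applies to the MSFC z-score and is only a guide for EDSS.

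**3. Chance of at least one false-positive visit, per outcome.** If visits were independent it would be 1 − 0.95⁸ = 33.7%, or 1 − 0.95⁴ = 18.5%. Changes from a shared baseline are correlated, so the real figure is lower. It was simulated under no treatment effect with t-tests on change and 33 per arm at every visit:

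| Assumed covariance | Eight visits | Four visits |
|---|---|---|
| AR(1), r to month 12 of 0.5, 0.7, 0.9 | 19.6%, 18.4%, 18.1% | 13.5%, 12.6%, 12.9% |
| Random intercept plus AR(1), same r | 20.8%, 19.2%, 18.3% | 13.8%, 12.8%, 12.7% |
| Compound symmetry | 25.1% | 15.6% |
| Patient-specific slopes plus noise | about 11% to 24% | about 10% to 16% |

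Slopes matter because section 1.1 describes SPMS as gradual accumulation of disability. When patients differ mainly in slope, the changes at successive visits move together and the chance falls. The overall range is roughly 11% to 25% for eight visits and 10% to 16% for four.

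**The case against.** The strongest reply is that nothing here is an error. Both tests are valid under randomisation, and the Wilcoxon test suits an ordinal EDSS. These are secondary endpoints of a 66-patient phase II trial, with no formal claim attached. Both are defined relative to baseline and 8.1.1 speaks of score differences, so baseline is probably already used by subtraction. Every visit is prespecified, and section 10 requires deviations to be described and justified. Most of this stands, and it is why the point is optional. It does not remove the point: subtraction is not covariate adjustment, and highlighting one visit would not be a deviation when none is named.

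Stronger readings are tempting but not supported:
- A reader might infer that the plan means to claim success on any significant visit. No section says so. Selective emphasis is a risk left open, not a planned rule.
- A reader might infer a large precision gain, particularly if raw follow-up scores were tested. The documents point to change scores and give no correlation; at r = 0.9 the gain is trivial.
- A reader might take about 18% as the minimum false-positive chance, as simple serial-correlation models suggest. With patient-specific slopes it can be near 11%.
- A reader might treat 8.1.1 as a regression plan that 10.2.2 fails to follow. It only describes what suits the scale.

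**Conclusion.** The point holds as a low-severity, optional improvement. Section 10.2.2 leaves available baseline information unused as a covariate and names no headline visit for MSFC or EDSS. If change scores are tested, adjustment would reduce the variance by 5% (r = 0.9) to 25% (r = 0.5), assuming equal variances. If every visit were read at two-sided 5%, at least one false-positive visit would arise in roughly 11% to 25% of null trials over eight visits, or 10% to 16% over four. The correlations, the covariance structures and the 5% level are assumptions, because the documents state none of them for these outcomes. The false-positive figures also assume 33 per arm at every visit.

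The conflict between 52 weeks and 2 years of follow-up affects only the visit count used here. That conflict, and the visit to which early-termination values belong, are separate matters and add no weight to this point.

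**What to change.** In 10.2.2, with the synopsis to match:

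1. MSFC z-score: ANCOVA of the month-12 score on arm and baseline score.
2. EDSS: one pre-named method, a baseline-adjusted rank-based ANCOVA at month 12. Do not allow a switch of model that depends on the data. With 33 per arm and half-point steps, a method that needs no category-by-category fit is the safer choice.
3. Name month 12 as the key visit for each outcome, in line with the Week 52 primary in sections 3.2.1, 10.2.1 and 10.4. Report it with the estimate and 95% CI where the method gives one.
4. Report all other visits as exploratory. This still meets the 3-monthly objective in section 2.2.

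The cost is a few sentences and a little programming, with no new data, visits or patients. The small downside is that no formal claim is made at visits other than month 12.
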